1.3 Exploratory objectives

[figure not shown]
The exploratory objectives of the study are:

- To evaluate the effect of treatment with CER-001 with respect to other efficacy measurements including carotid artery and carotid normalized wall index using 3T-MRI;
- To evaluate the effect of treatment with CER-001 with respect to potential surrogate markers on vessel wall biology including laboratory variables;
- To evaluate the effect of treatment with CER-001 with respect to inflammation;
- To evaluate plasma-mediated cellular Cholesterol efflux capacity;
- To measure ApoA-1 levels (pharmacokinetic parameters);
- To measure Cholesterols, triglycerides, lipids, apolipoprotein and lipoprotein levels (pharmacodynamics parameters).

2. Study summary

This is a phase III, multi-centre, randomized, 48 weeks, double-blind, parallel-group, placebo-controlled study to evaluate efficacy and safety of CER-001 on ApoA-1 and vessel wall area in patients with genetically defined familial primary hypoalphalipoproteinemia and receiving background optimized lipid therapy.

The study design is illustrated in the following figure:

3. Sample size

The assumptions upon which the power calculations are based are data from the 7 patients completing the CER-001-CLIN-007 SAMBA study, given the similarity of the genetic mutations. Those patients presented with a median value for MVWA of 25.0 mm² and had a follow-up median value at 6 months of 21.8 mm². The mean percent reduction is reported as 6.7%, standard deviation = 4.5%. These observed values would provide a conservative estimate of the effect of CER-001 in the more severe population for this FPHA study.

Using these results from SAMBA (i.e. an assumed standard deviation of 4.5%) and a 2:1 randomization scheme to maximize exposure to active drug, 16 completing patients in the CER-001 group and 8 in the placebo group (24 total completers for mITT) would yield 90% power to detect a difference from baseline versus placebo of 6.7%, using two-tailed testing with α =0.05. A total of 30 patients are planned to be randomized that would provide a buffer such that a 20% discontinuation rate would still allow the study to retain sufficient power for a supporting per protocol efficacy analysis (MVWA).

CER-001-CLIN-009 CER-001

4. Randomization

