7.4.1.1 Main analysis

A linear mixed model with repeated measures (MMRM) will be fitted to observed data for the mITT population without any imputation. An unstructured covariance matrix will be used to model random effects. The model will include the following variables:

- Change from baseline in carotid artery MVWA (mm², dependent variable)
- Randomized treatment group (CER-001 vs Placebo, independent variable)
- Genetic mutation (ABCA-1/ApoA-1/ABCA-1 and ApoA-1), independent variable)
- Carotid artery MVWA at W0 (mm², covariate)
- Visit (W8/W24/W48, independent variable)
- Treatment-by-Visit interaction (independent variable)
- Carotid artery MVWA at W0 by Visit interaction (independent variable)
- Treatment-by-carotid artery MVWA at W0 (independent variable)
- Subject (random factor)

Sample SAS Code

```
proc mixed data=DATASET method=reml covtest asycov alpha=0.05;

class USUBJID TRTGRP (ref="Placebo") VISIT (ref=LAST) GENETIC_MUT (ref="REF");

model CHANGE = BASELINE GENETIC_MUT BASELINE*VISIT TRTGRP VISIT

VISIT*TRTGRP BASELINE*TRTGRP / s ddfm=kr;

repeated visit / subject=USUBJID type=UN r rcorr;

lsmeans VISIT*TRTGRP / diff cl om e;

estimate "Treatment Effect" TRTGRP 1 -1 VISIT*TRTGRP 0 1 0 0 -1 0 / cl;

run;
```

Adjusted means in change from baseline for each treatment group (with 95%CI) as well as treatment effect (with 95%CI) at W24 will be provided. Treatment effect will be calculated as the difference in adjusted mean values for the two treatment groups at W24.

Adjusted means in change from baseline and treatment effect will also be estimated at W24 within each genetic mutation subgroup.

CER-001-CLIN-009 CER-001

A scatter plot will also be drawn representing the evolution of the carotid artery MVWA (mm²) according to the carotid artery MVWA at week 0 (mm²) grouped by treatment group.

Adjusted means (with 95%CI) of each randomized treatment group will also be plotted.

Results will be displayed according to table 5 of section 12.1.

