7.4.1.2 Supportive analysis

As a supportive analysis, the linear mixed model described in the previous section (7.4.1.1) will also be fitted to observed and imputed data for the mITT population. Thus, a multiple imputation procedure will be set up and is described below.

First, in case of non-monotone missing data pattern, a MI procedure will be applied using a MCMC algorithm to create 20 imputed datasets with a monotone missing data pattern. The number of burnin iterations before each imputation will be set to 200. Sample SAS code is displayed below.

Sample SAS Code

```
proc mi data=DATWIDE nimpute=20 seed=111 out=MONODAT;

var TRTGRP GENETIC_MUT BASELINE CHANGE8 CHANGE24 CHANGE48;

mcmc chain=MULTIPLE impute=MONOTONE nbiter=200;

run;
```

Second, the 20 datasets with a monotone missing data pattern will be fully imputed based on a monotone method. Corresponding sample SAS code is provided below.

Sample SAS Code

```
proc mi data= MONODAT nimpute=1 seed=222 out=MONODAT;

by _IMPUTATION_;

class TRTGRP GENETIC_MUT;

var TRTGRP GENETIC_MUT BASELINE CHANGE8 CHANGE24 CHANGE48;

monotone regression (CHANGE8 CHANGE24 CHANGE48);

run;
```

Finally, the linear mixed model described in section 7.4.1.1 will be applied for each complete data sets producing 20 analysis results. The final treatment effect estimate will be obtained combining these 20 estimates as follows:

CER-001-CLIN-009 CER-001

Sample SAS Code

```
proc mianalyze data=MRESULTS_;

modeleffects ESTIMATE;

stderr STDERR;

ods output parameterestimates=RESULTS_;

run;
```

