Preferred term 1	x (x	.x%)	x	(x.x%)	x	(x.x%)
	x (x	.x%)	х	(x.x%)	x	(x.x%)
Preferred term X	x (x	.x%)	x	(x.x%)	x	(x.x%)
System organ class 2	хх (х	к.х%)	хх	(xx.x%)	хх	(xx.x%)
	x (x	.x%)	х	(x.x%)	x	(x.x%)

Table 4 Concomitant treatments by Therapeutic Class and Preferred Term

Therapeutic class Preferred term	CER-001 N=xx		Placebo N=xx		Total N=xx	
At least one concomitant medication	хх	(xx.x%)	хх	(xx.x%)	хх	(xx.x%)
Therapeutic class 1	хх	(xx.x%)	хх	(xx.x%)	хх	(xx.x%)
Preferred term 1	x	(x.x%)	х	(x.x%)	x	(x.x%)
	x	(x.x%)	х	(x.x%)	x	(x.x%)
Preferred term X	х	(x.x%)	x	(x.x%)	x	(x.x%)
Therapeutic class 2	хх	(xx.x%)	хх	(xx.x%)	хх	(xx.x%)
	х	(x.x%)	х	(x.x%)	х	(x.x%)

Table 5 Adverse events by System Organ Class and Preferred Term

System Organ Class Preferred term	CER-001 term N=xx		Placebo N=xx		Total N=xx	
At least one AE	хх	(xx.x%)	хх	(xx.x%)	хх	(xx.x%)
System organ class 1	хх	(xx.x%)	хх	(xx.x%)	хх	(xx.x%)
Preferred term 1	х	(x.x%)	x	(x.x%)	x	(x.x%)
	х	(x.x%)	х	(x.x%)	х	(x.x%)
Preferred term X	х	(x.x%)	x	(x.x%)	х	(x.x%)
System organ class 2	хх	(xx.x%)	хх	(xx.x%)	хх	(xx.x%)
	х	(x.x%)	х	(x.x%)	х	(x.x%)

CER-001-CLIN-009

Table 6 Primary and secondary endpoints: linear mixed model with repeated measures for change in outcome xx from baseline to W8, W24 and W48

Independent variable Covariate	Parameter estimate	P-value	
Intercept	xx.x	x.xxx	
Genetic mutation			
ABCA-1	XX.X	X.XXX	
ApoA-1	XX.X	x.xxx	
ABCA-1 and ApoA-1	xx.x	x.xxx	
Baseline outcome xx	xx.x	x.xxx	
Interaction Baseline outcome * Visit			
W8	xx.x	x.xxx	
W24	xx.x	x.xxx	
W48	0.0		
Interaction Baseline outcome * Treatment			
CER-001	xx.x	x.xxx	
Placebo	0.0		
Visit			
W8	xx.x	x.xxx	
W24	xx.x	x.xxx	
W48	0.0		
Randomized treatment			
CER-001	xx.x	x.xxx	
Placebo	0.0		
Interaction Visit by Treatment			
W8 * CER-001	xx.x	x.xxx	
W24 * CER-001	xx.x	x.xxx	
W48 * CER-001	0.0		
W8 * Placebo	0.0		
W24 * Placebo	0.0		
W48 * Placebo	0.0		

CER-001-CLIN-009

Table 7 Primary and secondary endpoints: linear mixed model with repeated measures for change in outcome xx from baseline to W8, W24 and W48 – Changes adjusted for the model and treatment effect

	CER-001 LS-mean [95% CI] (p-value)	Placebo LS-mean [95% CI] (p-value)	Treatment effect Difference in LS-means [95% CI] (p-value)
	25 mean [55% oi] (p value)	25 mean [55% en] (p value)	erj (p varae)
Overall change in outcome x from baseline to:			
W8	xx.x [xx.x ; xx.x] (x.xxx)	xx.x [xx.x ; xx.x] (x.xxx)	xx.x [xx.x; xx.x] (x.xxx)

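### SAP 7.4.1.1: the sample-code contrast labelled as the treatment effect is evaluated at a baseline MVWA of 0 mm², and nothing in 7.4.1.2 stops that row being pooled

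*SAP*

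**What the plan says.** SAP 7.4.1.1 fits a repeated-measures mixed model to change in carotid MVWA at W8, W24 and W48. Baseline MVWA enters in mm², and the model line ends with "VISIT*TRTGRP BASELINE*TRTGRP / s ddfm=kr", so each arm has its own baseline slope. No centring of baseline is stated.

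The same sample code asks for the week-24 comparison twice:

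- through "lsmeans VISIT*TRTGRP / diff cl om e";
- through "estimate 'Treatment Effect' TRTGRP 1 -1 VISIT*TRTGRP 0 1 0 0 -1 0 / cl".

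The text defines the quantity wanted: "Treatment effect will be calculated as the difference in adjusted mean values for the two treatment groups at W24". The Table 7 template in 12.1 has the matching column, "Treatment effect Difference in LS-means [95% CI] (p-value".

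For the supportive analysis, 7.4.1.2 fits the model to 20 imputed datasets and says "The final treatment effect estimate will be obtained combining these 20 estimates as follows", followed by "proc mianalyze data=MRESULTS" and the generic column names ESTIMATE and STDERR. The input dataset appears nowhere else. The three MNAR scenarios (7.4.1.3.1) also combine 20 estimates each, and the per-protocol analysis (7.4.1.3.2) repeats 7.4.1.1 and 7.4.1.2.

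**The concern.** Once the treatment effect may vary with baseline, a treatment contrast must say at which baseline it is taken. The ESTIMATE statement does not, so it defaults to zero. SAP section 3 gives the planning value: "Those patients presented with a median value for MVWA of 25.0" mm². A wall area of 0 mm² lies far outside any plausible data, so the row is an extrapolation. Yet it carries the label the SAP uses for its primary result.

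If a programmer reports that row, or feeds it to the pooling step, the imputed analyses would estimate something other than the main analysis. They could then appear to contradict it, and the reader would blame the missing data when the cause was a contrast error.

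**Working it through.** **1. What the contrast estimates.** Write D(x) for the modelled W24 difference, CER-001 minus placebo, at baseline x. The intercept, mutation, visit, baseline and baseline-by-visit terms are shared by the arms and cancel, leaving

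D(x) = (T_CER − T_Pbo) + (TV_CER,24 − TV_Pbo,24) + x × (B_CER − B_Pbo),

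where T is treatment, TV treatment-by-visit and B the arm's baseline slope. The ESTIMATE statement gives coefficients to the first two brackets only, so it returns D(0). SAS sets an unlisted effect of this kind to zero. The contrast is estimable, so a number is printed without a warning. LSMEANS returns D(m), with m the mean baseline. Reading the coefficients as W24 assumes that VISIT sorts W8, W24, W48, as in the Table 6 template. The protocol's ANCOVA (12.2.1) lists no such interaction; without it D does not depend on x, and omitting the term would do no harm.

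**2. The plan's own power figure.** Inputs from SAP section 3: 16 and 8 completers, difference 6.7%, SD 4.5%, two-sided 0.05. Noncentrality = 6.7 / (4.5 × √(1/16 + 1/8)) = 3.44. With 22 df, power is 90.7%, against 90% stated. Scaled to 25.0 mm², the effect is 0.067 × 25.0 = 1.675 mm² and the SD is 0.045 × 25.0 = 1.125 mm².

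**3. Hand check of the standard errors.** Assumed, because the documents give neither: baseline CV 25% (SD 6.25 mm²) and between-visit correlation 0.5. For simplicity, both arms have the same baseline mean and variance.

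- Var D(m) = 1.125² × (1/16 + 1/8) = 0.237, so SE = 0.49 mm².
- Var of the slope difference (common to three visits) = 1.125² × (1 + 2 × 0.5)/3 × [1/(15 × 6.25²) + 1/(7 × 6.25²)] = 0.844 × 0.00536 = 0.00453.
- Var D(0) = 0.237 + 25² × 0.00453 = 3.07, so SE = 1.75 mm², 3.6 times larger.

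**4. Full grid, effect constant in mm².** GLS variance of the SAP model with randomly drawn baselines, CV 10-50% and correlation 0.3-0.7, power on 19 df:

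| | LS-means difference | ESTIMATE row |
|---|---|---|
| SE, mm² | 0.50-0.52 | 0.97-5.50 |
| Power | 87-89% | 6-40% |
| CV 25%, correlation 0.5: 95% CI half-width, mm² | about 1.1 | about 4.1 |
| CV 25%, correlation 0.5: power | 87-89% (whole grid) | 14% |

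The SE ratio is 1.9 to 10.7. At CV 25% and correlation 0.5 the ESTIMATE row's SE is 1.9-2.0 mm², a little above the hand value because drawn baselines are not perfectly balanced. With all 30 patients observed, the ratio is 1.9-10.1 and power 7-50% against 94-95%.

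**5. Simulated trials.** REML, unstructured covariance, 1000 trials per setting, correlation 0.5, t on 19 df, no Kenward-Roger correction. Effect constant in mm²:

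| Baseline CV | ESTIMATE row rejects | Rows differ on significance | Opposite signs |
|---|---|---|---|
| 10% | 8.8% | 82% | 35% |
| 25% | 17.9% | 73% | 17% |
| 40% | 26.3% | 63% | 12% |
| 50% | 36.8% | 55% | 7% |

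The LS-means difference rejects in 88-89% throughout. If the effect is instead proportional to baseline, D(0) is truly 0. The ESTIMATE row then rejects in 7-8% of trials against 86-89%, the rows differ on significance in 81-83%, and they have opposite signs in 46-51%. Under no effect the ESTIMATE row rejects in 6-8% and the LS-means row in 4-5%.

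**6. Independent check.** A separate build of the SAS design matrix used baseline means of 17.23 mm² (the earlier HoFH study, Protocol 3.3.2) and 25.0 mm², with assumed SDs of 3, 5 and 8 mm². It gave SE ratios of 2.2 to 7.5. Adding BASELINE*TRTGRP coefficients of +m and −m reproduced the LS-means difference exactly. In the simulations of step 5, centring baseline did the same, to within 1e-12 mm².

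**7. Which output fits the pooling code.** The ESTIMATE statement yields one row per imputation, 20 in all. The LSMEANS differences compare six treatment-by-visit cells, 6 × 5 / 2 = 15 rows per imputation, or 300 in all. Both tables carry estimate and standard-error columns. The MIANALYZE step has no filter or BY statement, so only the ESTIMATE output fits it without a selection step that the SAP does not describe.

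**The case against.** The strongest reply is that the documented analysis is correct. The text defines the effect as a difference in adjusted means, Table 7 reports it, and the LSMEANS line computes it, along with the W8 and W48 differences needed for 7.4.2.1. The TBR analysis (7.4.2.3) has the same kind of interaction and uses LSMEANS alone, which points to LS-means as the SAP's convention. The code is labelled as sample code, and other input datasets in it are not built either. Since 7.4.1.1 has defined the treatment effect, the text of 7.4.1.2 can be read as saying what to pool. Section 7.1.9 requires code review and double-programming, and 12.2 requires dry runs; a standard error several times too large should be noticed. All the figures above depend on a programming error occurring and on an assumed baseline spread.

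Most of this stands, and it limits the point: nothing is lost on the documented path, and the analyses exposed are supportive or sensitivity analyses. It does not remove the point. The ESTIMATE line is wrong as written and bears the name of the primary result. It is also the output that fits the pooling step unaltered, and a second programmer working from the same code can repeat it. The simulated 17.9% and the analytic 14% at CV 25% differ; the simulation omits the Kenward-Roger correction that the SAP specifies, so its rejection rates may run high. That does not affect the conclusion.

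**Conclusion.** The concern holds and should be fixed. The contrast labelled as the treatment effect is the W24 difference at 0 mm² and contradicts the SAP's own definition. The main analysis is sound if the text and Table 7 are followed. The live risk is in the supportive, MNAR and imputed per-protocol analyses, where the pooled dataset is undefined.

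If the wrong row were used, power would be about 6-40% for an effect constant in mm². For an effect proportional to baseline, the quantity estimated would be zero. The size rests on assumed baseline CV, between-visit correlation and shape of effect; the direction rests only on the algebra and on baseline being uncentred, as the SAP implies. The issue is the meaning and precision of the row. No clear type I error inflation was found.

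**What to change.** 1. In 7.4.1.1, do one of three things: centre baseline MVWA at the overall mean that LSMEANS uses; add BASELINE*TRTGRP coefficients of plus and minus that mean to the ESTIMATE statement; or delete the statement.
2. In 7.4.1.2, define MRESULTS_ as the W24 CER-001 minus placebo LS-means difference and its standard error, one row per imputation (20 rows). State that the MNAR scenarios and the imputed per-protocol analysis use the same definition.
3. Apply item 1 to the femoral model (7.4.2.2) wherever this code is reused. That section has no code of its own and no imputation, so item 2 does not apply there.

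A separate clerical point: 7.4.1.1 sends its results to table 5, which in 12.1 is the adverse-event template. The pointer should name Tables 6 and 7.

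The cost is a few lines of SAP code and text before database lock, with no new data and no change to the planned main result.

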7.4.2.2 Change from baseline in femoral artery MVWA

A linear mixed model with repeated measures (MMRM) will be fitted to observed data for the mITT population without any imputation. An unstructured covariance matrix will be used to model random effects. The model will include the following variables:

- Change from baseline in femoral artery MVWA (mm², dependent variable)
- Randomized treatment group (CER-001 vs Placebo, independent variable)
- Genetic mutation (ABCA-1/ApoA-1/ABCA-1 and ApoA-1), independent variable)
- Femoral artery MVWA at W0 (mm², covariate)
- Visit (W8/W24/W48, independent variable)
- Treatment-by-Visit interaction (independent variable)
- Femoral artery MVWA at W0 by Visit interaction (independent variable)
- Treatment-by-femoral artery MVWA at W0 (independent variable)
- Subject (random factor)

Analysis will be based on that described for the main analysis of the primary endpoint (section 7.4.1.1). No multiple imputation will be performed.

The following differences between placebo and the experimental treatment will be estimated:

- Change from baseline (W0) in femoral artery MVWA at 8 weeks
- Change from baseline (W0) in femoral artery MVWA at 24 weeks
- Change from baseline (W0) in femoral artery MVWA at 48 weeks.

These estimators will also be calculated within each genetic mutation.

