7.4.2.3 Change from baseline in target (plaque) to background (blood) ratio

An analysis of covariance (ANCOVA) will be fitted to observed data for the mITT population without any imputation. The model will include the following variables:

- Change from baseline (W0) in TBR based on standardized 18FDG uptake measured with 18FDG-PET/CT MVWA at 24 weeks (dependent variable)
- Randomized treatment group (CER-001 vs Placebo, independent variable)
- Genetic mutation (ABCA-1/ApoA-1/ABCA-1 and ApoA-1), independent variable)
- TBR at W0 (covariate)
- Interaction Treatment by TBR at W0 (independent variable)

Adjusted means for the change in TBR and the associated 95%CI will be provided for each randomized treatment group. Adjusted mean difference and the associated 95%CI will also be displayed.

CER-001-CLIN-009 CER-001

Sample SAS Code

```
proc glm data=DATWIDE alpha=0.05;
    class TRTGRP GENETIC_MUT;
    model CHANGE24 = BASELINE GENETIC_MUT BASELINE*TRTGRP TRTGRP / s;
    lsmeans TRTGRP / cl pdiff=control("REF");
run;
```

The previous statistics will also be estimated within each genetic mutation.

A scatter plot will be drawn representing the evolution of the TBR at week 24 according to the baseline TBR grouped by treatment group. Adjusted means (with 95%CI) for the change from baseline in each randomized treatment group will also be plotted.

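### Treatment effects per mutation subgroup are promised, but no model has a treatment-by-mutation term, so at any given baseline every subgroup gets the same CER-001 minus placebo difference

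*SAP*

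**What the plan says.** Protocol 12.2.1 promises treatment-effect confidence intervals for the ABCA-1 and ApoA-1 subgroups. Protocol 12.2.4 gives the purpose: to see whether the subgroups point in the same direction as the whole population. It adds that the study is not powered for them.

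The SAP repeats the promise for three endpoints:

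- Carotid MVWA (7.4.1.1): "Adjusted means in change from baseline and treatment effect will also be estimated at W24 within each genetic mutation subgroup".
- Femoral MVWA (7.4.2.2): "These estimators will also be calculated within each genetic mutation".
- TBR (7.4.2.3): "The previous statistics will also be estimated within each genetic mutation".

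In the carotid sample code the model statement begins "model CHANGE = BASELINE GENETIC_MUT BASELINE*VISIT TRTGRP VISIT". Its second line adds only visit-by-treatment and baseline-by-treatment. The femoral variable list has the same structure. The TBR code reads "model CHANGE24 = BASELINE GENETIC_MUT BASELINE*TRTGRP TRTGRP / s". SAP 7.1.8 says the mutation groups enter the primary and secondary models as an independent variable. SAP Table 6 has a block of rows for "Interaction Baseline outcome * Treatment" but none for treatment by mutation.

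The table that must hold the subgroup results is headed "Table 7 Primary and secondary endpoints: linear mixed model with repeated measures for change in outcome xx from baseline to W8, W24 and W48". It has separate rows, each with an interval and a p-value, for ABCA-1, ApoA-1 and double-mutation patients.

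**The concern.** A model with mutation as a main effect lets the mean change differ by mutation, but by the same amount in both arms. It has no parameter through which the treatment effect could differ by mutation. Subgroup rows taken from it would agree whatever the data show, and a reader could take that agreement as evidence that CER-001 works alike in both genotypes.

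The rows would also overstate precision. Each would carry the standard error of the whole-trial contrast, even for a subgroup of a few patients. Mutation is the stratification factor (SAP section 4), so these rows are likely to be read closely.

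**Working it through.** **1. The plan's own figure.** SAP section 3 gives 16 and 8 completers, difference 6.7%, SD 4.5%, two-sided alpha 0.05, power 90%.

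- SE = 4.5 × √(1/16 + 1/8) = 1.949.
- Noncentrality = 6.7 / 1.949 = 3.44, with 22 df.
- Power = 90.7%, which reproduces the stated 90%.
- 24 / (1 - 0.20) = 30 randomized, as stated.

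**2. The contrast, by algebra.** In the carotid model the expected change for mutation g, arm t (1 = CER-001, 0 = placebo), visit v and baseline b is

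μ + α_g + βb + γ_v + δ_v·b + τt + θ_v·t + λbt.

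Subtracting t = 0 from t = 1 at Week 24 leaves τ + θ_24 + λb. The mutation term α_g is gone. If two subgroups are evaluated at their own mean baselines b1 and b2, the rows differ by λ(b1 - b2), which is a baseline effect and not a mutation effect. For TBR the contrast is τ + λb, again without mutation.

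**3. Numerical check of the algebra.** The SAP design was built with its 12 fixed effects. The Week 24 contrast has coefficient 0 on both mutation parameters and is identical for the three groups at baselines of 20, 25 and 30 mm². Next, 500 trials were simulated under these assumptions: completers 8+4 / 6+3 / 2+1, SD 4.5 points, visit correlation 0.6, covariance treated as known, true effects -8 / 0 / +4.

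| Model | Mean estimates (three subgroups) | Standard errors |
|---|---|---|
| As specified | -3.54 / -3.54 / -3.54 (within-trial spread 0) | 2.07 for all |
| With mutation interactions (22 parameters) | -8.02 / -0.03 / +4.00 | 2.98 / 3.43 / 6.09 |

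**4. Size in mm².** The documents give 24 completers (16/8), SD 4.5%, effect 6.7% and a median MVWA of 25.0 mm² in the seven SAMBA patients. Assumed: the percentages apply to 25.0 mm², so SD = 0.045 × 25.0 = 1.125 and effect = 0.067 × 25.0 = 1.675; baseline SD 5 mm², with the same baseline distribution in both groups; no true treatment-by-baseline slope; visit correlation 0.5 or 0.8; no double-mutation patients; true Week 24 effect -1.675 in ABCA-1 and 0 in ApoA-1. The REML MMRM with unstructured covariance was fitted to 400 simulated trials per scenario.

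As a hand check, weight each subgroup by n1·n2/(n1 + n2). For 10:5 / 6:3 the weights are 50/15 = 3.33 and 18/9 = 2, so the pooled effect is 1.675 × 3.33/5.33 = 1.05.

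| Split ABCA-1 / ApoA-1 (CER-001:placebo) | Hand check (size) | Specified model, both rows | ApoA-1 95% CI half-width with interaction | Power for a 6.7-point interaction |
|---|---|---|---|---|
| 8:4 / 8:4 | 0.84 | -0.85 to -0.89 | about 1.5 | 37% |
| 10:5 / 6:3 | 1.05 | -1.04 to -1.05 | 1.7 to 1.8 | 35% |
| 12:6 / 4:2 | 1.26 | -1.26 to -1.27 | 2.1 to 2.2 | 29% |

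The half-width is t(18) times the mean model SE. Interaction power uses a noncentral t with 18 df. For 8:4 / 8:4, SE = 4.5 × √(1/8 + 1/4 + 1/8 + 1/4) = 3.90 and noncentrality = 6.7/3.90 = 1.72.

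At subgroup-specific mean baselines the two rows of the specified model differ by a median of only 0.08 to 0.13 mm², against a true gap of 1.675. With the interaction terms the averages are -1.67 to -1.75 (ABCA-1) and -0.04 to +0.01 (ApoA-1).

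**5. Would separate fits work?** A fit within one subgroup has 10 fixed effects and 6 covariance parameters. In 200 runs per size and correlation, failure was defined as rank deficiency or a covariance condition number above 10^4. Failures were 100% at 2:1, 99 to 100% at 4:2, and 0% at 6:3, 8:4 and 12:6. The 4:2 rate depends on that criterion.

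**The case against.** The strongest reply is that estimation within each subgroup may mean refitting the model separately by mutation, in which case the rows would differ. That is a natural reading of the phrase, but the SAP never states it, gives no code for it, and in 7.1.8 describes the groups as a model variable. Table 7 is also titled as the same mixed model. Separate fits would fail in small subgroups, so the SAP would have to say so in any case.

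Several narrower points have weight:

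- Table 8 also lacks a treatment-by-mutation row, but it omits the baseline-by-treatment term that 7.4.2.3 puts in the model. It is therefore not a complete list of terms and proves little. The case rests on the variable lists, the model statements, Table 6 and 7.1.8.
- The mm² scenario is constructed. Its splits, baseline SD and correlations come from outside the documents, and the pooled figures are essentially weighted averages of the inputs. They show scale only; the equality of the rows at a common baseline needs no such assumption.
- The analysis is exploratory and declared unpowered. SAP 7.4.3 summarises other MRI measures by mutation, and 7.7 lists individual data. However, carotid MVWA is not among the 7.4.3 summaries. Low power calls for wide intervals, not identical rows.
- The sponsor-approved dry runs in SAP 12.2 might expose the duplicate rows. That would be luck rather than specification.

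**Conclusion.** The concern holds. As written, the carotid MMRM, femoral MMRM and TBR ANCOVA cannot yield mutation-specific treatment effects, and their subgroup rows would be equal at any common baseline. That conclusion is algebraic and depends on no assumed figure. It does assume that the rows come from the printed models, which is the only reading the SAP supports.

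Under the stated illustration, a subgroup with no true effect would be reported with an average effect of -0.85 to -1.27 mm², with precision borrowed from the whole trial.

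The consequence is confined to supportive and exploratory results. The primary Week 24 estimate, its test and the 90% power figure do not change. This should be corrected before unblinding.

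**What to change.** Leave the primary model as it is, including baseline-by-treatment and the three mutation levels. For the subgroup rows only:

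1. Specify, before unblinding, one additional model per endpoint that adds TRTGRP*GENETIC_MUT. For the two MMRMs also add GENETIC_MUT*VISIT and TRTGRP*GENETIC_MUT*VISIT.
2. Evaluate the subgroup differences at one stated common baseline, such as the overall mITT mean.
3. Report the subgroup differences and the interaction estimate with 95% confidence intervals, labelled descriptive, and add the interaction rows to the table templates.
4. State a minimum number of patients per arm. A subgroup below it, as the double-mutation group may be, is listed patient by patient and left out of the additional model only. Its patients stay in the primary model.

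If the sponsor prefers simple descriptive summaries by mutation and arm, saying so and removing the model-based subgroup rows would also remove the contradiction in the SAP. The treatment-effect intervals promised in Protocol 12.2.1 would then have to be supplied another way or their omission recorded in SAP section 10.

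The cost is three extra models and a few table rows. The downside is wide intervals and only 29 to 37% power for a 6.7-point interaction at the splits above, which the protocol already accepts by calling the subgroups unpowered.
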